### 8.5.2 Pharmacokinetics

PK samples will be collected at the visits defined in the Assessment schedule ([Table 8-1](#)). Follow instructions outlined in the central laboratory manual regarding sample collection, numbering, processing and shipment. See the potential use of residual samples for more information.

In order to better define the PK profile, the timing of the PK sample collection may be altered based on emergent data and the expected PK for the drug(s) being tested.

Pharmacokinetic (PK) samples will be collected in all participants.

Commercially Confidential Information

Concentrations will be expressed in mass per volume units and will refer to the free base.

Commercially Confidential Information

Commercially Confidential Information

#### **8.5.4.1 Use of residual biological samples**

Residual blood samples may be used for another protocol specified endpoint.

Commercially Confidential Information

#### **8.5.5 Imaging**

##### **Magnetic resonance imaging (MRI) and magnetic resonance elastography (MRE)**

Participants will undergo magnetic resonance imaging twice during the course of the study (Baseline and End of Treatment) to quantitate liver fat. Optional exploratory MRI-based assessments (including MRE) will be performed in a subset of participants to evaluate the effect of treatment on exploratory MRI related endpoints as outlined in [Table 2-1](#) (Objectives and related endpoints).

All participants who discontinue prematurely on or after Week 8 must have an end of treatment MRI assessment.

MRI acquisition sequences, including MRE, are described in MRI Participant Scanning Guide.

The coded medical images will be used primarily for analysis as described in this protocol; however, the images may also be used for the development and evaluation of new analysis methods directly related to the area of research that this study covers.

## **9 Discontinuation and completion**

### **9.1 Discontinuation from study treatment and from study**

#### **9.1.1 Discontinuation from study treatment in individual participants**

Discontinuation of study treatment for a participant occurs when study treatment is permanently stopped for any reason (prior to the planned completion of study drug administration) and can be decided by either the participant or the investigator.

Study treatment must be discontinued under the following circumstances:

1. Participant decision
2. Pregnancy
3. Use of prohibited treatment(s)
4. Any situation in which study participation might result in a safety risk to the participant
5. The investigator believes that continuation would negatively impact the safety of the participant or the risk/benefit ratio of trial participation

6. Hypersensitivity (CTCAE Grade 2 or higher) reaction to study medication
7. An adverse event that is CTCAE Grade 4 or higher, regardless of whether the event is suspected to be related to study drug(s)
8. An adverse event that is CTCAE Grade 3 and suspected to be related to study drug(s) (apart from liver and renal events - see below)
  - If a liver or renal event occurs, follow guidelines outlined in [Section 16.1](#) and [Section 16.2](#), respectively, regarding discontinuation of study treatment
9. Any laboratory abnormalities that in the judgment of the investigator, taking into consideration the participant's overall status, prevents the participant from continuing participation in the study

If discontinuation of study treatment occurs, the investigator should make a reasonable effort to understand the primary reason for the participant's premature discontinuation of study treatment and record this information.

Participants who discontinue from study treatment agree to return for the end of treatment assessments (i.e., EOS1 or EOS2) indicated in the Assessment schedule ([Table 8-1](#); and refer to [Section 8](#)).

If the participant cannot or is unwilling to attend any visit(s), the study staff should maintain regular telephone contact with the participant, or with a person pre-designated by the participant. This telephone contact should preferably be done according to the study visit schedule.

After discontinuation from study treatment, at a minimum, in abbreviated visits, the following data should be collected at visits or via telephone/email contact:

- new / concomitant treatments
- adverse events/Serious Adverse Events

The investigator must also contact the IRT to register the participant's discontinuation from study treatment.

### **9.1.2 Discontinuation from study**

Discontinuation from study is when the participant permanently stops receiving the study treatment, and further protocol-required assessments or follow-up, for any reason.

If the participant agrees, a final evaluation at the time of the participant's study discontinuation occurs should be made as detailed in the assessment table (refer to [Section 8](#)).

### **9.1.3 Lost to follow-up**

For participants whose status is unclear because they fail to appear for study visits without stating an intention to discontinue from study treatment or discontinue from study or withdraw consent/oppose to the use of their data/biological samples, the investigator must show "due diligence" by documenting in the source documents steps taken to contact the participant, e.g., dates of telephone calls, registered letters, etc. A participant should not be considered as lost to follow-up until due diligence has been completed or until the end of the study.

## **9.2 Withdrawal of informed consent/Opposition to use data/biological samples**

Withdrawal of consent/opposition to use data/biological samples occurs when a participant:

- Explicitly requests to stop use of their biological samples and/or data (opposition to use participant's data and biological samples), and
- No longer wishes to receive study treatment, and
- Does not want any further visits or assessments (including further study-related contacts)

In this situation, the investigator should make a reasonable effort (e.g., telephone, e-mail, letter) to understand the primary reason for the participant's decision to withdraw his/her consent/opposition to use data/biological samples and record this information.

Where consent to the use of Personal and Coded Data is not required in a certain country's legal framework, the participant therefore cannot withdraw consent. However, they still retain the right to object to the further collection or use of their Personal Data.

Study treatment must be discontinued and no further assessments conducted, and the data that would have been collected at subsequent visits will be considered missing.

Further attempts to contact the participant are not allowed unless safety findings require communicating or follow-up.

If the participant agrees, a final evaluation at the time of the participant's withdrawal of consent/opposition to use data/biological samples should be made as detailed in the [Assessment schedule](#) (please also refer to [Section 8](#)).

Novartis will continue to retain and use all research results (data) that have already been collected for the study evaluation, including processing of biological samples that has already started at the time of consent withdrawal/opposition. No new Personal Data (including biological samples) will be collected following withdrawal of consent/opposition.

### **9.2.1 Study stopping rules**

#### **Treatment arm stopping rules**

If any of the following events occur, all ongoing treatment arms sharing the same suspect drug(s) will be placed on hold to further enrollment, and no new participants may be dosed, however dosing of those without safety concerns may continue. In addition, a full review of all available clinical safety data and discussion with the investigators will take place.

- One participant on study drug experiences any adverse event that is CTCAE Grade 4 or higher that is suspected to be related to study drug(s)
- Two participants on study drug experience a similar adverse event that is a CTCAE Grade 3 or higher other than ALT elevation regardless of whether the events are suspected to be related to study drug(s)
- Two participants are discontinued due to a liver event as defined in [Section 16.1](#)
- Two participants are discontinued due to a renal event as defined in [Section 16.2](#)

- Two participants meet the same individual participant stopping rule 6, 7, or 8 ([Section 9.1.1](#))
- One participant experiences any adverse event that is CTCAE Grade 5 regardless of whether the event is suspected to be related to study drug(s)
- One participant experiences an SAE that is suspected to be related to study drug(s)
- The Principal Investigator and Sponsor consider that the number and/or severity of adverse events justify discontinuation of the suspect drug(s)
- The Sponsor unilaterally requests it

Safety reviews for treatment arm stopping will be conducted cooperatively between medically qualified representatives of the sponsor and investigator and a joint decision will be made. The treatment arm may resume following the safety review, if the investigator and sponsor agree it is safe to proceed.

#### **9.2.2 Early study termination by the sponsor**

The study can be paused or terminated by Novartis at any time for any reason. This may include reasons related to the benefit/risk assessment of participating in the study, practical reasons (including slow enrollment), or for regulatory or medical reasons. In taking the decision to terminate, Novartis will always consider the participant's welfare and safety. Should early termination be necessary, participants must be seen as soon as possible and treated as a participant who discontinued from study treatment. The investigator may be informed of additional procedures to be followed in order to ensure that adequate consideration is given to the protection of the participant's interests. The investigator or sponsor depending on the local regulation will be responsible for informing IRBs/IECs of the early termination of the trial.

### **9.3 Study completion and post-study treatment**

Each participant will be required to complete the study in its entirety and thereafter no further study treatment will be made available to them.

For participants who discontinue the study early and do not return for a study completion visit, a safety follow-up call will be conducted 30 days after last administration of study treatment. The information collected is kept as source documentation. All SAEs reported during this time period must be reported as described in [Section 10.1.3](#) and the SOM. Documentation of attempts to contact the participant should be recorded in the source documentation.

Trial-level study completion is defined as when final data analysis and reporting, and appropriate closeout activities are completed, following either triggering event:

1. When the final participant in the fifth cohort finishes his/her Study Completion visit, and any repeat assessments associated with this visit have been documented and followed-up appropriately by the investigator, or
2. When an early study termination decision is finalized.

## 10 Safety monitoring, reporting, and committees

### 10.1 Definition of adverse events and reporting requirements

#### 10.1.1 Adverse events

An adverse event (AE) is any untoward medical occurrence (e.g., any unfavorable and unintended sign [including abnormal laboratory findings], symptom or disease) in clinical investigation participant after providing written informed consent for participation in the study. Therefore, an AE may or may not be temporally or causally associated with the use of a medicinal (investigational) product.

The investigator has the responsibility for managing the safety of individual participant and identifying adverse events.

Novartis qualified medical personnel will be readily available to advise on trial related medical questions or problems.

The occurrence of adverse events must be sought by non-directive questioning of the participant at each visit during the study. Adverse events also may be detected when they are volunteered by the participant during or between visits or through physical examination findings, laboratory test findings, or other assessments.

Adverse events must be recorded under the signs, symptoms or diagnosis associated with them, accompanied by the following information (as far as possible) (if the event is serious, refer to [Section 10.1.2](#)):

1. the Common Toxicity Criteria (CTC) AE grade (version 5.0 or higher) for the adverse event. If CTC-AE grading does not exist for an adverse event, use:

- 1 = mild
- 2 = moderate
- 3 = severe
- 4 = life threatening\* (see [Section 10.1.2](#) for definition of a serious adverse event [SAE])

\*Note: There may be cases where a CTCAE with a grade of 4 (life-threatening) may not necessarily be an SAE (e.g., certain laboratory abnormalities in the absence of meeting other seriousness criteria).

- 5 = death

2. its relationship to the study treatment
3. its duration (start and end dates or ongoing) and the outcome must be reported
4. whether it constitutes a SAE (see [Section 10.1.2](#) for definition of SAE) and which seriousness criteria have been met
5. action taken regarding with study treatment
6. its outcome i.e., its recovery status or whether it was fatal

All adverse events must be treated appropriately. Treatment may include one or more of the following:

- Dose not changed

- Dose reduced/increased
- Drug interrupted/permanently discontinued

Conditions that were already present at the time of informed consent should be recorded in medical history of the participant.

Adverse events (including lab abnormalities that constitute AEs) should be described using a diagnosis whenever possible, rather than individual underlying signs and symptoms.

Adverse event monitoring should be continued for at least 5 half-lives following the last dose of study treatment or until the final study visit, whichever is longer.

Once an adverse event is detected, it must be followed until its resolution or until it is judged to be permanent (e.g., continuing at the end of the study), and assessment must be made at each visit (or more frequently, if necessary) of any changes in severity, the suspected relationship to the interventions required to treat it, and the outcome.

Information about adverse drug reactions for the investigational drug can be found in the Investigator's Brochure (IB).

Abnormal laboratory values or test results constitute adverse events only if they fulfill at least one of the following criteria:

- they induce clinical signs or symptoms
- they are considered clinically significant
- they require therapy

Clinically significant abnormal laboratory values or test results must be identified through a review of values outside of normal ranges/clinically notable ranges, significant changes from baseline or the previous visit, or values which are considered to be non-typical in participants with the underlying disease.

Follow the instructions found in the SOM for data capture methodology regarding AE collection for participants that fail screening.

### **10.1.2 Serious adverse events**

An SAE is defined as any adverse event (appearance of [or worsening of any pre-existing]) undesirable sign[s], symptom[s] or medical condition[s]) which meets any one of the following criteria:

- fatal
- life-threatening
  - Life-threatening in the context of a SAE refers to a reaction in which the participant was at risk of death at the time of the reaction; it does not refer to a reaction that hypothetically might have caused death if it were more severe (please refer to the ICH-E2D Guidelines).
  - results in persistent or significant disability/incapacity
  - constitutes a congenital anomaly/birth defect
  - requires inpatient hospitalization or prolongation of existing hospitalization, unless hospitalization is for:

- routine treatment or monitoring of the studied indication, not associated with any deterioration in condition
- elective or pre-planned treatment for a pre-existing condition that is unrelated to the indication under study and has not worsened since signing the informed consent
- social reasons and respite care in the absence of any deterioration in the participant's general condition
- treatment on an emergency outpatient basis for an event not fulfilling any of the definitions of a SAE given above and not resulting in hospital admission
- is medically significant, e.g., defined as an event that jeopardizes the participant or may require medical or surgical intervention to prevent one of the outcomes listed above

Medical and scientific judgment should be exercised in deciding whether other situations should be considered serious reactions, such as important medical events that might not be immediately life threatening or result in death or hospitalization but might jeopardize the participant or might require intervention to prevent one of the other outcomes listed above. Such events should be considered as "medically significant." Examples of such events are intensive treatment in an emergency room or at home for allergic bronchospasm, blood dyscrasias or convulsions that do not result in hospitalization or development of dependency or abuse.

All malignant neoplasms will be assessed as serious under "medically significant" if other seriousness criteria are not met.

Any suspected transmission via a medicinal product of an infectious agent is also considered a serious adverse reaction.

All reports of intentional misuse and abuse of the product are also considered serious adverse event irrespective if a clinical event has occurred. Please see [Section 10.1.5](#) for more details.

### **10.1.3 SAE reporting**

To ensure participant safety, every SAE, regardless of causality, occurring after the participant has provided informed consent and until 30 days after the last study visit must be reported to Novartis safety immediately, without undue delay, under no circumstances later than within 24 hours of learning of its occurrence. Detailed instructions regarding the submission process and requirements are to be found in the investigator folder provided to each site. Information about all SAEs is collected and recorded on the Serious Adverse Event Report Form; all applicable sections of the form must be completed in order to provide a clinically thorough report.

For patients who sign the pre-screening informed consent form, SAEs which occur after signature of this consent will only be captured if they are reported to be causally related to study procedures (i.e., blood sampling).

SAEs occurring after the participant has provided informed consent until the time the participant is deemed a screen failure must be reported to Novartis.

All follow-up information for the SAE including information on complications, progression of the initial SAE and recurrent episodes must be reported as follow-up to the original episode within 24 hours of the investigator receiving the follow-up information. An SAE occurring at a

different time interval or otherwise considered completely unrelated to a previously reported one must be reported separately as a new event.

If the SAE is not previously documented in the Investigator's Brochure or Package Insert (new occurrence) and is thought to be related to the study treatment, a Novartis Chief Medical Office and Patient Safety (CMO&PS) associate may urgently require further information from the investigator for health authority reporting. Novartis may need to issue an Investigator Notification (IN) to inform all investigators involved in any study with the same study treatment that this SAE has been reported.

Suspected Unexpected Serious Adverse Reactions (SUSARs) will be collected and reported to the competent authorities and relevant ethics committees in accordance with EU Guidance 2011/C 172/01 or as per national regulatory requirements in participating countries.

Any SAEs experienced after the 30 day period after the last study visit should only be reported to Novartis Safety if the investigator suspects a causal relationship to study treatment, unless otherwise specified by local law/regulations.

#### **10.1.4 Pregnancy reporting**

If a female trial participant becomes pregnant, the study treatment must be stopped, and the pregnancy consent form should be presented to the trial participant. The participant must be given adequate time to read, review, and sign the pregnancy consent form. This consent form is necessary to allow the Investigator to collect and report information regarding the pregnancy.

To ensure participant safety, each pregnancy occurring after signing the informed consent must be reported to Novartis within 24 hours of learning of its occurrence. The pregnancy should be followed up to determine outcome, including spontaneous or voluntary termination, details of the birth, and the presence or absence of any birth defects, congenital abnormalities, or maternal and/or newborn complications.

Pregnancy should be recorded and reported by the investigator to the Novartis CMO&PS department. Pregnancy follow-up should be recorded on the same form and should include an assessment of the possible relationship to the study treatment any pregnancy outcome. Any SAE experienced during pregnancy must be reported.

If a female partner of a male trial participant who took study treatment in this study becomes pregnant, pregnancy outcomes should be collected. Consent to report information regarding these pregnancy outcomes should be obtained from the mother.

After consent is provided, the pregnancy reporting will occur up to one year after the estimated date of delivery (EDD).

#### **10.1.5 Reporting of study treatment errors including misuse/abuse**

Medication errors are unintentional errors in the prescribing, dispensing, administration or monitoring of a medicine while under the control of a healthcare professional, participant, or consumer (EMA definition).

Misuse refers to situations where the medicinal product is intentionally and inappropriately used not in accordance with the protocol.

Abuse corresponds to the persistent or sporadic, intentional excessive use of a medicinal product, which is accompanied by harmful physical or psychological effects.

Study treatment errors and uses outside of what is foreseen in the protocol will be recorded on the appropriate CRF irrespective of whether or not associated with an AE/SAE and reported to Safety only if associated with an SAE. Misuse or abuse will be collected and reported in the safety database irrespective of it being associated with an AE/SAE within 24 hours of Investigator's awareness.

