**Table 10-1      Guidance for capturing the study treatment errors including misuse/abuse**

Treatment error type	Document in Dosing CRF (Yes/No)	Document in AE eCRF	Complete SAE form
Unintentional study treatment error	Yes	Only if associated with an AE	Only if associated with an SAE
Misuse/Abuse	Yes	Yes	Yes, even if not associated with a SAE

For more information on AE and SAE definition and reporting requirements, please see the respective sections.

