## 6 Statistical methods for Efficacy/Pharmacodynamic (PD) parameters

All participants within the efficacy/PD analysis set will be included in the efficacy/PD data analysis.

Data will be excluded from the efficacy/PD analyses in the following cases:

- For participants with protocol deviations affecting the efficacy/PD analyses, the data will be excluded as described in [Table 4-1](#) above.
- For participants that discontinued treatment early, the following *programming rule* will be applied: *Any efficacy assessments that occurred on or after the treatment discontinuation study day, will be excluded from all efficacy/PD data analyses. An exception to this is the Day 85 visit or EOS visit imaging data (MRI and MRE assessments), that will be excluded only if they occurred prior to study day 56 (i.e., imaging assessments that occurred on or after study day 56, will not be excluded from the imaging analyses).*
- Participants with <80% treatment compliance

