### Treatment compliance calculation

For each subject, the treatment compliance (%) will be calculated using the following formula:

$$100 * \left( \frac{\text{Number of capsules expected to be taken up to the last treatment day} - \text{Number of capsules missed during the treatment period}}{\text{Number of capsules expected to be taken up to the last treatment day}} \right)$$

where,

*Number of capsules expected to be taken up to the last treatment day =*  
last treatment day \* CCI , if treated with LYS006

OR

last treatment day \* CCI , if treated with LJN452

*Number of capsules missed during the treatment period =*  
Sum (Number of capsules expected to be taken in the dosing modification period x - Number of capsules actually taken in the dosing modification period x)

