#### Notes:

- The treatment compliance will be calculated separately for each treatment (LYS006 and LJN452).
- The last treatment day is defined as the last available start or end treatment day, as reflected in the dosing dataset.

- A dose modification period is a period with either a dose change or a dose interruption. These periods will be identified in the dosing dataset under records with TYPE OF CHANGE='DOSE CHANGED' and TYPE OF CHANGE='DOSE INTERRUPTED', respectively.
- For the dose modification periods:
  - Only the dosing records with non-missing dose administered, non-missing start date and non-missing end date will be considered in the calculations.
  - Dose administered = Number of capsules administered
  - The number of capsules expected to be taken in a dosing modification period =  
(period end day – period start day +1) \* CCI , if treated with LYS006  
OR  
(period end day – period start day +1) \* CCI , if treated with LJN452
  - The number of capsules actually taken in a dosing modification period =  
(period end day – period start day +1) \* dose administered
  - The frequency of dose administered will not be considered in the calculations, only the dose administered itself.

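### The SAP's compliance formula sums signed differences, so recorded intake above plan can offset missed capsules and keep a participant in the efficacy/PD analyses

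*Protocol*

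**What the plan says.** **The filter.** SAP section 6 lists the cases in which data leave the efficacy/PD analyses. One is "Participants with <80% treatment compliance". There is a lower limit only.

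**The score.** Under the SAP heading Treatment compliance calculation, compliance is the expected capsules up to the last treatment day minus the missed capsules, as a percentage of the expected capsules. The missed capsules are "Sum (Number of capsules expected to be taken in the dosing modification period x - Number of capsules actually taken" in that period, added over periods. The Notes give capsules taken as the length of the period times the dose administered. No term is floored at zero or capped at the planned count, and the percentage has no ceiling.

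**The records that enter.** The Notes say "A dose modification period is a period with either a dose change or a dose interruption", found through the type-of-change field (dose changed or dose interrupted). Records need a dose, a start date and an end date. Dosing frequency is ignored, and LYS006 and LJN452 are scored separately.

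**What the protocol sends to the dosing data.** Section 10.1.5 states: "Study treatment errors and uses outside of what is foreseen in the protocol will be recorded on the appropriate CRF". Table 10-1 answers yes in its Dosing CRF column both for unintentional errors and for misuse or abuse. The section's definition of abuse, "Abuse corresponds to the persistent or sporadic, intentional excessive use of a medicinal product", is narrower than excess intake in general, because it continues with a requirement of harmful effects. The general sentence and Table 10-1 are therefore the better link to the SAP.

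**The concern.** The SAP calls the term capsules missed, but the formula computes a net shortfall. A dose-change period with more capsules than planned contributes a negative number of missed capsules, which is subtracted from capsules truly missed in other periods.

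Two participants with the same missed days could then be treated in opposite ways: the one with no other deviation is excluded, and the one who also took too much on other days is kept. With around 20 evaluable participants expected per arm (protocol section 5), one such participant is 1/20 = 5% of an arm in the ELF, ALT and liver-fat analyses. Nothing in the score or in the one-sided limit marks intake well above 100%.

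**Working it through.** The documents give no worked compliance figure, so there is none to reproduce. The check applies the SAP formula to assumed dosing patterns.

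**Inputs**
- Treatment days T: 84 (Day 1 plus the self-administered supply for Days 2 to 84 in the Table 8-1 footnotes). T = 85 is also run, because Table 8-1 marks a dose on Day 85.
- Planned capsules per day: redacted. The count cancels when over-use is expressed as a multiple of the planned daily count.
- Assumptions, not document figures: M fully missed days, and O days at f times the planned count. All are recorded in periods that enter the sum, for one drug.

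**Formulas**
- As written: score = 100 × (T − [M − O × (f − 1)]) / T
- Floored at zero in each period: score = 100 × (T − M) / T
- Over-use days needed to reach 80% as written: O ≥ (M − 0.2 × T) / (f − 1), rounded up

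**Twenty missed days, double capsules (f = 2)**
- T = 84, O = 0: 64/84 = 76.2%, excluded
- T = 84, O = 3: 67/84 = 79.8%, excluded
- T = 84, O = 4: 68/84 = 81.0%, kept
- T = 85, O = 0: 65/85 = 76.5%, excluded
- T = 85, O = 3: 68/85 = 80.0%, kept, because the rule removes only scores below 80%

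**Fewest over-use days that lift a participant to 80% or more (T = 84; T = 85 in brackets)**

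| Missed days | Floored score | f = 1.5 | f = 2 | f = 3 |
|---|---|---|---|---|
| 20 | 76.2% (76.5%) | 7 (6) | 4 (3) | 2 (2) |
| 30 | 64.3% (64.7%) | 27 (26) | 14 (13) | 7 (7) |
| 42 | 50.0% (50.6%) | not reachable | 26 (25) | 13 (13) |

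Without over-use, the most missed days that still pass is 16 for T = 84 (68/84 = 81.0%) and 17 for T = 85 (68/85 = 80.0%). At f = 2 each further missed day needs one more double-capsule day.

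**What a pass can mean.** With T = 84, 30 missed days and 14 doubled days, the score is (84 − 30 + 14)/84 = 81.0%. At least the planned dose was taken on 54/84 = 64.3% of days, and exactly the planned dose on 40/84 = 47.6%.

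**No ceiling.** No missed days and 10 doubled days score 94/84 = 111.9%, which passes without any mark.

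**With the floor.** Twenty missed days score 76.2% (T = 84) or 76.5% (T = 85) whatever the over-use, and the participant is excluded.

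**The case against.** A reader might infer that over-use automatically carries poorly compliant participants through the filter. The documents do not support that, for several reasons.

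- **Coding is open.** Only dose-changed and dose-interrupted records with complete fields enter the sum. Table 10-1 names the Dosing CRF but does not say that an error or misuse entry becomes a dose-changed record. The modifications planned in protocol 6.5.1 and Table 6-3 are interruption, reduction and return to the starting dose. None exceeds plan, so a conforming modification cannot produce a negative term.
- **Some over-use never counts.** Frequency is ignored, so extra intakes at the usual capsule count give no credit. Excess of one drug cannot offset gaps in the other.
- **Another rule covers long gaps.** In SAP Table 4-1, deviation TRT03 removes efficacy/PD data from its study day onwards when an interruption exceeds 2 days.
- **Over-use is visible elsewhere.** Study drug administration is listed by participant (SAP 8.2). Misuse and abuse are always handled as serious adverse events (protocol 10.1.2 and Table 10-1). Pill counts are checked at each visit (protocol 6.6.1).
- **A net sum has a meaning.** It measures total intake against total plan, and it credits a genuine catch-up dose.

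The first four points stand and narrow the concern, but they do not remove it. The SAP does not restrict a dose change to a reduction, so a day at double the count fits its wording. TRT03 leaves scattered gaps of 2 days or less, and data from before the deviation, to the 80% rule. Under Table 10-1 an unintentional error without an adverse event need appear only in the Dosing CRF. Visibility in a listing does not change the score. On the last point, the SAP names the quantity capsules missed and uses it as an exclusion rule, and a net total does not measure that.

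**Conclusion.** The concern holds in a conditional form. As written, the formula can credit intake above plan against missed capsules of the same drug and lift a participant over the 80% limit. Four double-capsule days are enough for 20 missed days over 84 days (3 over 85), and 14 (13 over 85) for 30 missed days.

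This rests on over-use being stored as a dose-changed record with complete dates and a capsule count above plan, and on the missed days not being removed by TRT03. It therefore matters mainly for scattered short gaps and for data before a TRT03 deviation. The documents give no frequency of over-use, so the realised effect may be nil. If it occurs, each affected participant is about 5% of an arm of 20.

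The filter applies to the efficacy/PD analyses of a non-confirmatory study. The primary safety analysis does not use it. This is a cheap correction to a derivation and does not put the study's main conclusion in doubt.

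**What to change.** In SAP section 6, define missed capsules as the sum over dose modification periods of max(0, expected − taken), separately for each drug as now. With that floor compliance cannot exceed 100%, so no separate cap is needed. Derive excess capsules, the sum of max(0, taken − expected), as a separate variable and list it by participant. State how intake above plan is coded in the dosing dataset.

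The cost is one changed line in the derivation, one derived variable and one listing. No new data are needed. A small downside is that a genuine catch-up dose would no longer offset a missed day. If the sponsor wants such days credited, the SAP should say so explicitly.
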